7.1 Data analysis

We will obtain HVR and S under control conditions (HVRc and Sc) and under rocuronium conditions at TOF 0.6 (HVRr and Sr). The ratio of HVRr/HVRc and Sr/Sc will be calculated. This will give an indication of the effect of rocuronium on respiratory muscles per se ($\text{Sr/Sc} = S'$) and on the combined effect of rocuronium on respiratory muscles and carotid bodies ($\text{HVRr/HVRc} = \text{HVR}'$). To compute the effect of rocuronium on just the

carotid bodies F' is calculated which is the ratio of HVR'/S' . In other words the effect of rocuronium on hypercapnic ventilation is used to correct for the effect of rocuronium on respiratory muscles (as well as other influences such as drowsiness, discomfort, etc). A value of $F' < 1$ is the effect of rocuronium on the carotid bodies. See also Eriksson et al. 1993.

The dynamics of return of the HVR towards control values following reversal is our main end-point. We are aware that the absolute value of the HVR is contaminated by effects from the respiratory muscles next to an effect of rocuronium at the carotid bodies. However, the calculation made on HVR and S obtained before and during rocuronium infusion give us an indication on the distribution of muscle vs. carotid body effects. We will take this into account in our analysis. The HVR-time data will be analyzed by taking time, HVR and TOF ratio into account. This HVR-time data will be analyzed using an exponential function allowing assessment of a half-life for HVR return (and hence for return of carotid body function). The HVR-TOF ratio data will be analyzed by linear regression and allows assessment whether HVR return follows TOF ratio or whether it deviates from the TOF ratio.

7.2 Sample size calculation

We decided not to use a crossover design as we do not want to expose one person to multiple awake rocuronium infusions. Hence we chose a parallel design. We powered the study on the speed of reversal of HVR from TOF ratio 0.6 to TOF ratio 1.0 between sugammadex and neostigmine. Assuming a return of carotid body function within 3-5 min for sugammadex and at least 10-20 min for neostigmine with a SD of the difference of 4-5 min we calculate the need for 12 subjects per group giving a power of > 90% ($\alpha = 0.05$). The power calculation was performed in SigmaPlot.

8. Monitoring

The subject will be closely monitored by measurement of the TOF ratio using the TOFF Cuff/TOF watch system, oxygen saturation, respiratory rate, tidal volume, and ECG. In case of an emergency sugammadex will be administered to overcome the muscle blockade.

9. Subject discomfort

Due to the mild level of relaxation some subjects may experience some muscle weakness and dysarthria. This is frequently seen in postoperative patients and is well accepted, especially when subjects are well coached during the period of mild muscle relaxation. In case the subject indicates that his discomfort is unacceptable the level of

relaxation will be reduced, as discussed in paragraph 6. In case the subjects demands termination of the study the reversal agent Sugammadex will be administered.

There are multiple studies on the use of muscle relaxants in volunteers, such as the Eriksson et al. (1993) study. Here we give some examples:

Schuller et al. **Response of bispectral index to neuromuscular block in awake volunteers.** Br J Anaesth 2015; 115: i95-i103: Rocuronium 0.7 mg/kg was administered causing full paralysis in unsedated volunteers.

Blokland et al. **Detection of attempted movement from the EEG during neuromuscular block: proof of principle study in awake volunteers.** Sci Rep 2015; 5:12815: Complete relaxation in awake volunteers. Study performed at RadboudMC.

Cedbøg et al. **Pharyngeal function and breathing pattern during partial neuromuscular block in the elderly: effects on airway protection.** Anesthesiology 204; 120: 312-25: TOF ratios of 0.7 in elderly (>70 yrs) unsedated volunteers.

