Sugammadex and neostigmine are both reversal agents of neuromuscular blockade. At LUMC we use both agents in clinical practice but remain without knowledge on their effects on carotid body function. Our current proposal is designed to study items 1 and 2 in healthy awake volunteers.

2. Study objectives

To assess (i) the effect of partial neuromuscular blockade (NMB; TOF ratio 0.8 and 0.6) induced by low-dose rocuronium on the ventilatory response to isocapnic hypoxia and (ii) the effect over time (from TOF 0.6 to TOF 1.0) of the reversal by sugammadex, neostigmine or placebo in healthy volunteers.

To assess the effect of partial NMB (TOF ratio 0.6) induced by low-dose rocuronium on the ventilatory response to hypercapnia and effect over time (from TOF 0.6 to TOF 1.0) of the reversal by sugammadex, neostigmine or placebo in healthy volunteers.

3. Hypotheses

- A. Rocuronium will induce impairment of carotid body function through blockade of cholinergic neurotransmission in carotid bodies resulting in a reduced or absent ventilatory response to isocapnic hypoxia.
- B. Sugammadex will completely restore carotid body function following rocuronium administration with full reversal of the ventilatory response to isocapnic hypoxia within 2 min.
- C. Neostigmine will cause a protracted reversal of the carotid body function following rocuronium administration with full reversal within 40-60 min.

4. Volunteers

We will study 30 healthy male volunteers. They will be randomized to receive low-dose rocuronium followed by one of three reversal treatments: placebo (normal saline), neostigmine (1 mg) or sugammadex (2 mg/kg). All volunteers will receive a physical examination prior to enrollment.

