4.3 Drop out and replacements

Subjects that drop out will be replaced by a new subject. A subject may terminate the study at any moment, and will then receive sugammadex 2 mg/kg to ensure full reversal of the neuromuscular blockade. Subjects will then be paid (5 euros/h participation).

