4.5 Pre-study requirements

All subjects will be asked to refrain from food 6 hours prior to the study and from drinks 2 hours prior to the study.

5. Study design

This is a randomized, double blind, 3-arm, placebo controlled parallel study on the influence of reversal of a partial NMB on carotid body function following rocuronium administration. Healthy volunteers will be randomized to receive either placebo (Group1, n = 12), neostigmine (1 mg, n = 12) or sugammadex (2 mg/kg, n = 12) following a continuous rocuronium infusion for 120 min aimed at a TOF ratio of 0.8 for 1 h followed by 0.6 for another hour. Prior to the rocuronium infusion and during the infusion, ventilatory responses to isocapnic 2-min hypoxic pulses will be obtained as well as the (hyperoxic) ventilatory response to hypercapnia. After the 120 min infusion and the administration of reversal agents, the ventilatory response to hypoxic pulses will be obtained at 5 min interval for at least 60 min. In case the response has not returned to pretreatment control values, additional responses will be obtained. Hereafter, a final ventilatory response to carbon dioxide will be obtained (at hyperoxic conditions).

All procedures will be executed in compliance with the current revision of the Declaration of Helsinki and Good Clinical Practice guidelines. The trial starts after the medical ethical committee has approved the study protocol and will have a maximum duration of one year.

5.1 Rocuronium administration:

We will titrate rocuronium to effect followed by a target controlled infusion aimed at a TOF ratio of 0.8 and 0.6 (see Fig. 1). After 120 min the continuous infusion will be terminated. The plasma concentration and expected TOF ratio is simulated in Figure. 1.

[figure not shown]

Figure 1. Simulated plasma concentration (LEFT) and expected TOF ratio (RIGHT). A continuous infusion of rocuronium for 120 min (1st hours aimed at TOF ratio 0.8, 2nd hour TOF ratio 0.6). Additionally during the 1 hour period after reversal the timing of hypoxic challenges are given (vertical dotted lines).

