After approval of the protocol by the Human Ethics Committee a total of 30 volunteers will be recruited and tested in the Clinical Research Unit of the Department of Anesthesiology at Leiden University Medical Center. Each volunteer will undergo a physical examination first and only healthy volunteers without a (family) history of neuromuscular disease will be included in the study.

The subjects are not allowed to eat or drink for at least 8 hours before the experiment.

After arrival in the laboratory all subjects will be connected to monitors including ECG, pulse oximeter and two EMG electrodes to measure diaphragmatic EMG activity; next an iv line is placed. The subjects are comfortably seated in a semirecumbant position. Next, the control ventilatory responses are obtained. A facemask will be used to administer specific gas mixtures.

Following the control ventilator responses and after a short break the rocuronium will be titrated to a TOF ratio of 0.8 for 1 hour followed by 0.6 for the next hour. In case the TOF ratio of 0.6 has a large effect on the subject in terms of oxygen saturation (values < 94%) or increases in end-tidal $\text{PCO}_2 > 9 \text{ kPa}$, we will increase the TOF ratio to 0.7 and if this has no effect to 0.8. The experiment is then continued. After the desired TOF ratio is reached, the ventilatory challenges are repeated. The TOF ratio will be measured with the TOF Cuff/TOF watch device at 25 mA. We know from experience that this is an acceptable current.

After the 120-min infusion, the subject is reversed with either placebo (normal saline), or neostigmine 1 mg, or sugammadex 2 mg/kg. We will then repeat the 2-min hypoxic challenges at 5 min interval. When the hypoxic response has returned to control values but not before 60 min have elapsed since reversal we will perform one final hypercapnic ventilatory response.

We expect that all values will normalize within 90 min. The iv line is then removed and after another break of 1 hours (observation period) the subjects is discharged.

The duration of one single experiment is about 4 hours (incl. post experiment observation period). The complete study requires 30 experiment days and will last about 6 months (incl. data analysis)

7. Data and sample size calculation

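### The plan gives two incompatible sample sizes, 30 volunteers in total and 12 in each of three arms (36), and claims power above 90% only for 12 per arm

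*Combined protocol and SAP*

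**What the plan says.** Two totals stand in the current text of the combined protocol and SAP.

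**Thirty in total.** Section 4 (Volunteers): "We will study 30 healthy male volunteers". Section 6 (Study procedures): "a total of 30 volunteers will be recruited and tested", and later "The complete study requires 30 experiment days".

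**Twelve per arm.** Section 5 (Study design) describes the trial thus: "This is a randomized, double blind, 3-arm, placebo controlled parallel study". It then gives the group sizes: "placebo (Group1, n = 12), neostigmine (1 mg, n = 12) or sugammadex (2 mg/kg, n = 12". Section 7.2 (Sample size calculation) reports "we calculate the need for 12 subjects per group giving a power of > 90" per cent at alpha 0.05, for the speed of recovery of the hypoxic response on sugammadex against neostigmine. The inputs are ranges for the time to recovery: "within 3-5 min for sugammadex and at least 10-20 min for neostigmine with a SD of the difference of 4-5 min".

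On attrition, Section 4.3 says: "Subjects that drop out will be replaced by a new subject".

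**The concern.** Three arms of 12 make 36, not 30. Each figure appears more than once: 30 as two headcounts and a matching count of experiment days, 12 per arm in the design and in the power calculation. A reader cannot dismiss either as a single slip.

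The total is the number of healthy people the ethics committee is asked to let receive rocuronium while awake, and it tells the team when recruitment is complete. Two people following this protocol could stop at different points. Stopping at 30 misses the number that the plan says it needs, and no section gives a power for 30.

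**Working it through.** **1. The totals.** 3 × 12 = 36. The gap is 36 − 30 = 6, and 6/36 = 17%. If 30 were divided equally, 30/3 = 10 per arm. The plan never states that split, so it is an assumption in what follows.

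**2. Readings that might reconcile the totals.**
- *36 enrolled, 30 completing.* Section 4.3 replaces drop-outs, and Section 6 applies 30 to those recruited as well as tested.
- *Unequal arms, 12/12/6, keeping the two powered arms whole.* Section 5 gives placebo n = 12.
- *Some volunteers studied twice.* Section 7.2 rejects a crossover and chooses parallel groups.

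None of them works.

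**3. Reproducing 12 per arm.** Inputs from Section 7.2: sugammadex 3–5 min, neostigmine 10–20 min (worded as a minimum), SD 4–5 min, alpha 0.05. The test and sidedness are not given, so I assume a two-sample t-test, two-sided. With standardized difference d = gap/SD per arm and n per arm, power is the probability that a noncentral t variable with 2n − 2 degrees of freedom and noncentrality d·√(n/2) falls beyond the two-sided 5% critical value.

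Two input sets inside the stated ranges give 12 as the smallest n reaching 90%:

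| Gap (min) | SD | d | n = 12 | n = 11 | n = 10 |
|---|---|---|---|---|---|
| 10 − 3 = 7 | 5 per arm | 7/5 = 1.40 | 90.6% | 87.7% | 84.1% |
| 10 − 5 = 5 | 5 for a difference, so 5/√2 = 3.54 per arm | 5/3.54 = 1.414 | 91.1% | 88.4% | 84.8% |

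For the first row, the noncentrality is 1.40 × √6 = 3.43 at n = 12 and 1.40 × √5 = 3.13 at n = 10.

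So the plan's 12 is reproducible, and under the inputs that reproduce it, 10 per arm falls below 90%.

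**4. The same result without choosing a gap or SD.** The d needed for 90% power is 1.385 at n = 12, 1.454 at n = 11 and 1.534 at n = 10. If 12 is the smallest n that reaches 90%, d lies between 1.385 and 1.454, and power at 10 per arm is then 83.4–86.7%. With one-sided alpha 0.05 the corresponding range is 84.3–87.2%.

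**5. Elsewhere in the stated ranges** (SD taken per arm, two-sided):

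| Gap (min) | SD (min) | n = 12 | n = 10 |
|---|---|---|---|
| 5 | 5 | 64.9% | 56.2% |
| 7 | 4.5 | 95.4% | 90.8% |
| 8 | 5 | 96.3% | 92.2% |
| 15 − 4 = 11 (midpoints) | 4.5 | above 99.9% | 99.9% |

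On an even grid over the three ranges (41 × 81 × 21 points), power exceeds 90% in 90.2% of combinations at 10 per arm and in 95.4% at 12. If the SD is read as that of a difference, the shares are 99.9% and 100%.

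**The case against.** The strongest reply is that the conflict is clerical and that 30 would probably be enough. Section 7.2 says 12 per arm gives more than 90%. It does not say in terms that 12 is the smallest such number, and the band of d for which 12 is minimal covers only about 2% of the grid. Ten per arm keeps power above 90% over about nine tenths of the stated combinations, and over nearly all of them if the SD is read as the plan words it. The neostigmine time is given as a minimum, so a grid capped at 20 min is conservative.

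This stands as far as it goes: the plan does not show that 30 is underpowered, and the 84–85% figures should be read as conditional. It does not remove the contradiction. Section 7.2 presents 12 per group as a need. If 10 suffice, that statement is wrong; if it is right, 30 is too few.

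Two smaller points are also fair. The unnamed test, SD type and sidedness would be a reporting gap even with a consistent total. And 36 experiment days follows only if one volunteer is studied per day, which Section 6 implies but does not state.

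**Conclusion.** The concern holds. Sections 4 and 6 set 30; Sections 5 and 7.2 set 36; nothing reconciles them. The 17% shortfall against the plan's own calculation needs no assumption beyond recruitment stopping at 30.

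The loss of power is uncertain. Assuming an equal split and a two-sided two-sample t-test, it is about 6 percentage points (from 90.6–91.1% to 84.1–84.8%) for the two input sets that yield exactly 12, while power stays above 90% over most of the stated ranges. Because Section 7.2 gives ranges and not the values entered, the reader cannot tell which case applies. The point must be fixed because the total sample size is a basic design figure and the two values cannot both be followed.

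**What to change.** Use one total throughout, in one of two ways.

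- **Adopt 36.** Write 36 volunteers (3 × 12) in Sections 4 and 6, and bring the number of experiment days in Section 6 into line (36 if one volunteer is studied per day). This costs six more volunteers, and up to six more days, than those sections now state. It is the number that the plan's own calculation gives.
- **Adopt 30.** Write n = 10 per arm in Sections 5 and 7.2 and restate the power, recomputed from the values actually entered in SigmaPlot. This costs wording and one recalculation.

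In either case, Section 7.2 should name the single difference, the single SD (per arm or of a difference), the test and the sidedness, so that the stated power can be reproduced.

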10. SAFETY

10.1 Adverse Events

An adverse event (AE) is any untoward medical occurrence in a patient or clinical investigation subject administered a pharmaceutical product, including placebo, and which does not necessarily have to have a causal relationship with treatment. An AE can be:

- Any unfavorable and unintended sign (including an abnormal laboratory finding), symptom, or disease temporally associated with the use of study medication, whether or not considered related to the study medication.
- Any new disease or exacerbation of an existing disease.
- Any deterioration in protocol-required or non-protocol-required measurements of laboratory value or other clinical tests (e.g. ECG or X-ray) that results in symptoms, a change in treatment, or discontinuation from study medication.
- Recurrence of an intermittent medical condition (e.g. headache) not present at baseline.

Subjects with AEs that are ongoing at the subject's completion/discontinuation visit (last treatment visit) will be followed up for 7 days and the follow up information will be recorded in the CRF. New AEs that are reported in the 7 days following the subject's completion/discontinuation visit will be recorded in the AE section of the CRF. Any AE that is still ongoing 7 days after the completion/discontinuation visit will have an end date of 'ongoing' in the CRF, however the investigator will continue to follow up ongoing AEs and record information in the source documents. SAEs will be followed until the event resolves or the event or sequels stabilize and this information will be reported to the Sponsor, local and central ethics committees using the SAE Data Form.

10.2 Reporting of Adverse Events

For subjects who receive study medication, all AEs (learned through spontaneous reports, subject interview) starting from providing informed consent for study participation through the period beyond study completion will be collected on the AE pages of the CRF. In addition, a note should be made in the source documentation of the subject. For each AE on the AE pages of CRF, the following information will be recorded: AE (e.g. headache), start date, start time, stop time, severity, study medication action taken, other action taken, relationship to study medication, outcome, seriousness. A cluster of signs and symptoms that results from a single cause should be reported as a single AE (e.g. fever, elevated WBC, cough, abnormal chest x-ray, etc. can all be reported as "pneumonia.").

10.3 Criteria for Assessing Severity

The Investigator will evaluate the comments of the subject and the response to treatment in order that he/she may judge the true nature and severity of the AE.

Severity refers to the accumulated intensity of discomfort/impairment of health since the last recording of AEs and will be assessed according to the following criteria:

Mild: Awareness of sign, symptom, or event, but easily tolerated.

Moderate: Discomfort enough to cause interference with usual activity and may warrant intervention.

Severe: Incapacitating with inability to do usual activities or significantly affects clinical status and warrants intervention.

The criteria for assessing severity are different to those used for seriousness (see below for the definition of an SAE).

10.4 Criteria for Assessing Causality

The question of the relationship of an AE to study medication should be determined by the Investigator after thorough consideration of all facts that are available. Assessment of causality is based on considering associative connections (time or place), pharmacological explanations, previous knowledge of the drug, presence of characteristic clinical or pathological phenomena, exclusion of other causes, and/or absence of alternative explanations.

The causal relationship of an AE to study medication will be assessed according to the following criteria (based on World Health Organization definitions):

Not related: Temporal relationship to study medication administration is missing or implausible, or there is an evident other cause.

Related

Unlikely to be related: Temporal relationship to study medication administration makes a causal relationship improbable; and other drugs, chemicals, or underlying disease provide plausible explanations.

Possibly related: Reasonable time sequence to administration of study drug, but event could also be explained by concurrent disease or other drugs or chemicals. Information on drug withdrawal may be lacking or unclear.

Probably related: Reasonable time sequence to administration of study drug, but unlikely to be attributed to concurrent disease or other drugs or chemicals, and which follows a clinically reasonable response on withdrawal (dechallenge). Rechallenge information is not required.

Definitely related: Plausible time relationship to study medication administration; event cannot be explained by concurrent disease or other drugs or chemicals. The response to withdrawal of the drug (dechallenge) should be clinically plausible. The event must be definitive pharmacologically or phenomenologically, using a satisfactory re-challenge procedure if necessary.

10.5 Serious Adverse Events

A serious adverse event (SAE) is any untoward medical occurrence that at any dose:

- Results in death;

- Is life-threatening (i.e. the subject was at immediate risk of death from the AE as it occurred. This does not include an event that, had it occurred in a more severe form or was allowed to continue, might have caused death);
- Requires inpatient hospitalization or prolongation of existing hospitalization;
- Results in persistent or significant disability/incapacity;
- Is a congenital anomaly/birth defect (in the child of a subject who was exposed to the study medication);
- Is a medically important event or reaction (see below).

Other important medical events that may not be immediately life-threatening or result in death or hospitalization but may, based on appropriate medical judgment, jeopardize the subject or require intervention to prevent one of the outcomes in the definition of SAE listed above should also be considered SAEs. Examples of such events are intensive treatments in an emergency room or at home for allergic bronchospasm, blood dyscrasias or seizures that do not result in hospitalization, or development of drug dependency or drug abuse. These events may be considered to need rapid reporting by the Sponsor to competent authorities.

All SAEs, including those occurring up to 7 days following the subject's completion/discontinuation visit (subject's last treatment visit), will be recorded on the AE pages of the CRF. In addition, SAEs must be reported to the Sponsor, local and central ethics committees using the SAE Data Form (Sponsor), letter (local ethics committee) and CCMO website (central ethics committee). Subjects with SAEs must be followed until the event resolves or the event or sequels stabilize.

